12.2 Statistical analysis plan

12.2.1 Estimated sample size and expected recruitment

Aggregation of NHS hospital-level audit data collected by PLAN and data for Greater London from the Office for National Statistics [ONS 2014] and Health & Social Care Information Centre [HSCIC 2014] confirms an annual expected birth rate of approximately 150,000 per annum across the maternity units in the Greater London area. Direct data, collected by PLAN from these units, covering 209,982 deliveries indicates that 4,027 GAs were provided to facilitate maternal delivery over the same time period; this is equivalent to a GA proportion of 1.92% (95% CI 1.86% – 1.98%) for all deliveries.

Given the expected annual birth rate of approximately 150,000, we therefore expect approximately 2,880 GA deliveries (95% CI 2,685 – 3,075) over a given 12 month data collection period. Patients undergoing non-LSCS obstetric surgery under GA (e.g. manual removal of placenta) will also be eligible for inclusion: based upon the same audit data this is expected to increase the total number of eligible patients by a factor of 1.12 to 3,225 (95% CI 3008 – 3444) per annum.

We aim to recruit at least 70% of all eligible patients – equivalent to a point estimate of ~2250 included participants over 12 months. Some women will be ineligible to participate due to the inclusion criteria (e.g. must be English speaking). We also expect a proportion of eligible women to decline involvement and the total number of recruitment hospital sites to vary, hence the final included number of participants may be lower or higher than this point estimate.

This is a descriptive observational study with the intent of capturing data from as many eligible participants over a 12 month study period as possible. The power of the expected sample size to exclude the possibility of not detecting an incidence of “Brice positive” AAGA that is at least three times the incidence described in the overall surgical patient population (taken as 0.15% or 1:660 [Sandin 2000]) using an exact binomial test and one-sided α of 0.05 is 88%.

Analysis and post hoc power calculations will be taken at the 12 month threshold, with a view to potentially extending the study dependent upon the confidence interval width of the identified AAGA proportion and ability to make a statistically significant comparison between previously documented incidences for AAGA.

No formal estimate is made for the sample size of the baseline comparator group of non-AAGA patients who will be undergoing PTSD screening at 30 days. A lack of clear evidence regarding PTSD prevalence in patients receiving general anaesthesia for obstetric surgery would make such estimations speculative. Therefore, sample size has been preferentially determined by operational issues and consideration of sample size of studies identified in a previous systematic review of post-natal PTSD [Anderson 2012].

12.2.2 *Primary endpoint analysis*

The proportion of obstetric GA patients reporting AAGA will be expressed using binomial confidence intervals and compared with established values (see above for rectification of sample size).

There are three competing hypotheses. First, that the event proportion of Brice positivity in obstetrics is similar to that of the general population (i.e. ~1:660). If so, then we expect ~4 patients (binomial 95% CI 1 – 10). Second, that our incidence of Brice positivity will be similar to Paech’s already reported incidence (i.e. ~1:152 [Paech 2008]). Then we expect ~15 (95% CI 8 – 25) patients. Third, that the ratio between “Brice positive” and spontaneous reporting as in the general population (i.e. 1:660 vs 1:19,000) is maintained for obstetric patients (i.e. ~1:19). Then we expect 118 patients (95% CI 98 – 141). These figures for each of the three possible outcomes will be compared using Fisher’s exact test or chi-squared testing to yield a definitive answer as to which is the most likely hypothesis of the three.

Because we are administering the Brice questionnaire during 0-24h following the index GA (i.e. as soon as possible after GA recovery), we expect to obscure those cases who may otherwise report spontaneously. In other words, we do not expect by our methods to detect spontaneous reporting as such, as the questions will already have been asked. It is possible that some few patients may telephone in after their discharge to report that they now recall AAGA, perhaps triggered by the study, but even that would not fulfil the criterion for spontaneous reporting. We plan to class any such cases as “triggered reporting” and analyse them separately.

Subgroup analysis of the AAGA proportion will be conducted for type and urgency of surgical procedure (including emergency LSCS), de novo conversion from regional anaesthesia to GA and for GA inductions using propofol vs. thiopental.

12.2.3 *Secondary endpoint analysis*

For secondary outcomes of interest, data will be presented as a number or percentage; mean and standard deviation (SD) for normally distributed data and median and interquartile range (IQR) for non-parametric data, with 95% confidence intervals (CI). Significance of associations with anaesthetic, surgical and patient factors will be tested using relevant measures of correlation. If sufficient AAGA events are identified, then a multivariable regression model will be used to evaluate the independent association of specific anaesthetic episode variables with AAGA, with results expressed as odds ratios (ORs).

Post-Traumatic Stress Disorder Checklist (PCL-5) results will be expressed as a total symptom severity score (range = 0-80), obtained by summing the scores from each of the 20 checklist items. PCL-5 questions are grouped into 4 domains referring to different symptom criteria: 5 questions refer to symptoms of re-living (cluster B), 2 to avoidance behaviour (cluster C), 7 to emotional blunting (cluster D) and 6 to symptoms of hyper-excitability (cluster E). Symptoms are considered significant when the person scores 2 or more on the item. Women will be considered positive on the PCL-5 when they have at least 1 significant symptom for cluster B, at least 1 for cluster C, at least 2 cluster D items and 2 cluster E [Blevins 2015, National Centre for Posttraumatic Stress Disorder]. PTSD prevalence rates will be estimated for the entire sample and certain subgroups, including AAGA and non-AAGA patients. Results will be expressed with the respective 95% confidence intervals. Fischer's exact test will be used to test the homogeneity of prevalence rates in the subgroups.

Case descriptions of the experiences of AAGA undergone by patients with AAGA will be presented in anonymised format. The phase of anaesthesia/surgery when the AAGA event occurred, alongside possibility contributory, causal or mitigated factors, will be described where possible.

13 Direct access to source data

The Investigator(s)/institution(s) will permit study-related monitoring, audits, REC review, and regulatory inspection(s), providing direct access to source data/documents. Study participants are informed of this during the informed consent discussion. Participants will consent to provide access to their medical notes.

14 Ethics and regulatory requirements

Before any site can enrol patients into the study, the Principal Investigator must be granted written NHS R&D approval – confirmation of capacity and capability.

The site must conduct the study in compliance with the protocol, as agreed by the Sponsor and as given favourable opinion by the Research Ethics Committee (REC) and HRA.

The Chief Investigator will be provided (via the Sponsor) with file indices E.G. JREODOC0003 TMF index and JREODOC0004 ISF index for use with SOP JREOSOP0019 'Preparation and Maintenance of the TMF' The CI will be responsible for the maintenance of the TMF and may delegate the responsibility of ISF file maintenance to the PI at each participating site.

It is the responsibility of the Principal Investigator at each site to ensure that all subsequent amendments gain the necessary R&D approval. Refer to JREOSOP0011 'Management of Amendments'.

Within 90 days after the end of the study, the CI and Sponsor will ensure that the REC is notified that the study has finished. If the study is terminated prematurely, those reports will be made within 15 days after the end of the study. Refer to JREOSOP0015 'End of study declaration'.

The CI will supply an End of Study report of the clinical study to the REC within one year after the end of the study. The sponsor can provide JREODOC0059 End of Study report template.

The primary ethical issue in any obstetric study is to ensure the welfare of the mother and the baby take priority over any research aims. The psychosocial and physical vulnerability of mothers should always be considered. This study does not involve any physical intervention that could cause any harm or stress. The Brice questionnaire is short and has been designed with the intention that it does not present any significant risk or burden to the patient. However, the patient is under no obligation to participate and complete the questionnaires if they do not wish to.

One consideration of an adverse effect may be that by encouraging a patient to recall if they dreamed or not during the operation, then adverse memories may be triggered at a sensitive time. However, since this questionnaire has been used previously with no report of ill effects, we are confident that the risk of stress induced by the questions is low. In fact, it could certainly be considered advantageous to address the issue of awareness early, whilst a patient is still under the care of the hospital team, rather than to allow symptoms of illness, discomfort or adverse memories to go unexplored and unexplained or to emerge at a later time.

Patients who experience AAGA will benefit from a structured protocol for follow up and provision of support services by local clinical teams.

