7.2 Exclusion criteria

- Patients too unwell or confused to be able to complete the questionnaire
- Patient refusal
- General anaesthesia for non-obstetric indication (e.g. colorectal or orthopaedic surgery in a pregnant patient)
- Surgery ≥ 48 hours post-partum
- Unable to communicate verbally/in writing in English language

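### The target of about 2,250 is labelled 70% of eligible patients but is 70% of all expected obstetric general anaesthetics in Greater London, and the 88% power quoted for it is not the exact-test power

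*Protocol*

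**What the plan says.** Protocol section 12.2.1 builds the target in four steps.

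- Births: audit and national data give a figure that "confirms an annual expected birth rate of approximately 150,000 per annum across the maternity units in the Greater London area".
- GA rate: the network's audit, "covering 209,982 deliveries indicates that 4,027 GAs were provided to facilitate maternal delivery over the same time period", gives 1.92%.
- GA deliveries: "we therefore expect approximately 2,880 GA deliveries (95% CI 2,685 – 3,075) over a given 12 month data collection period".
- Other obstetric surgery under GA is then expected to "increase the total number of eligible patients by a factor of 1.12 to 3,225 (95% CI 3008 – 3444) per annum".

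The recruitment aim follows: "We aim to recruit at least 70% of all eligible patients – equivalent to a point estimate of ~2250 included participants over 12 months". The synopsis repeats 2,250 as the target number.

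Only after this does the section say: "Some women will be ineligible to participate due to the inclusion criteria (e.g. must be English speaking"). It adds that some eligible women will decline, that the number of sites may vary, and that the final number may fall on either side of the estimate. Section 7.2 excludes women who meet "Unable to communicate verbally/in writing in English language" and "Patients too unwell or confused to be able to complete the questionnaire". Section 7.1 requires age 18 or over and at least 24 weeks' gestation.

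The same section states 88% power at the expected sample size, using an exact binomial test at one-sided 0.05, for an incidence at least three times a reference of 0.15% (1:660).

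**The concern.** The count from which 70% is taken is called eligible, but it is a count of procedures. The section then says that some of the women in it are not eligible. The 70% and the 2,250 therefore cannot both be right for the stated catchment. Either the uptake required of eligible women is above 70%, or the expected sample is below 2,250.

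Three things rest on the number. The first is the 88% power. The second is the set of expected event counts in section 12.2.2 (about 4, 15 and 118, which match 2,250/660, 2,250/152 and 2,250/19). The third is the benchmark against which recruitment would be judged: a site approaching and consenting 70% of its eligible women would appear to be on target while contributing less than its share of 2,250.

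**Working it through.** **Reproducing the target (inputs from section 12.2.1)**

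- GA rate: 4,027 / 209,982 = 1.92%.
- GA deliveries: 150,000 × 1.92% = 2,880.
- All obstetric GAs: 2,880 × 1.12 = 3,225.6, stated as 3,225.
- Target: 0.70 × 3,225 = 2,257.5, stated as about 2,250. Conversely, 2,250 / 3,225 = 69.8%.

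The chain reproduces. No step removes women for age, gestation, language, illness or confusion.

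**Applying an eligible share first**

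The protocol gives no eligible share, so the shares below are assumptions. With eligible share s, the expected sample is 0.70 × s × 3,225. The uptake among eligible women needed for 2,250 is 2,250 / (s × 3,225).

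| Assumed s | Eligible women | Sample at 70% uptake | Uptake needed for 2,250 |
|---|---|---|---|
| 95% | 3,064 | 2,145 | 73% |
| 90% | 2,902 | 2,032 | 78% |
| 80% | 2,580 | 1,806 | 87% |

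The direction is certain for any s below 100%. Only the size is unknown.

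**Power of the stated test**

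The rule is to reject at the smallest r for which P(X ≥ r | n, p0) ≤ 0.05. Power is P(X ≥ r | n, p1), with p1 = 3 × p0. The protocol gives the reference both as 0.15% and as 1:660, so both are shown.

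| n | Reject at | Actual alpha (0.15%; 1:660) | Power (0.15%; 1:660) |
|---|---|---|---|
| 2,250 | 8 or more | 0.022; 0.023 | 79.1%; 80.0% |
| 2,145 | 7 or more | 0.046; 0.048 | 84.7%; 85.4% |
| 2,032 | 7 or more | 0.036; 0.037 | 80.7%; 81.4% |
| 1,806 | 7 or more | 0.021; 0.022 | 70.2%; 71.2% |

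The stated 88% does not reproduce at 2,250. Two other calculations give about 88%. Rejecting at 7 or more events gives 87.8% or 88.4%, but the actual alpha is then 0.056 or 0.058, above the stated 0.05. A one-sided normal approximation gives 88.0% with 0.15%.

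Power does not fall steadily as n falls, because the critical value drops from 8 to 7 a little below 2,200. With 70% uptake, power is lasting below its value at 2,250 once n falls to about 1,995. That corresponds to 1 − 1,995 / (0.70 × 3,225) = 11.6%, or roughly 12% ineligible.

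**The case against.** The strongest reply is that the 70% was meant to absorb ineligibility as well as refusal, since the sentences that follow it mention both. On that reading 2,250 stands and only the word eligible is loose. This is a fair reading, and the first option under the fix adopts it. It does not clear the text, because the label is then wrong and the uptake needed among eligible women is higher than stated.

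A reader might go further and infer that the design cannot deliver its sample. The protocol does not support that:

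- The 70% is stated as a minimum.
- Section 12.2.1 says the final number may be lower or higher, and allows an extension after the 12-month analysis.
- Section 6 opens the study to any NHS hospital with maternity services, while 3,225 covers Greater London only.
- Sections 8 and 9.1 let women missed or too unwell in the first 24 hours be approached later, so not all of them are lost.
- No ineligible share is given.

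None of these enters the calculation, so they bear on whether the number is reached, not on whether it is correctly described.

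A reader might also infer that ineligibility is what pulls power below 88%. That does not hold either. The exact test already falls short at 2,250, and exact power is higher at 2,145 and slightly higher at 2,032 than at 2,250.

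Finally, this is a descriptive cohort whose main result is a proportion with a binomial confidence interval. A somewhat smaller sample widens that interval but does not bias it. That limits the weight of the point.

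**Conclusion.** Section 12.2.1 is wrong as written on two counts.

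First, about 2,250 is 70% of all expected obstetric GAs in Greater London, not of eligible women. Seventy per cent of eligible women in that catchment is fewer: 2,145, 2,032 or 1,806 under assumed eligibility of 95%, 90% or 80%. Those sizes depend wholly on the assumed shares; the direction does not. This is a misstated recruitment basis, not evidence that the study will miss its number.

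Second, and independently, the 88% is not the power of the stated test. At 2,250 the exact one-sided 5% test has 79–80% power. Over the assumed range it is about 85%, 81% and 70–71%. Ineligibility by itself has an uneven effect on power and becomes clearly harmful only above roughly 12%.

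**What to change.** Correct section 12.2.1, and the synopsis if the number changes, in one of two ways:

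1. Keep 2,250 and describe it as about 70% of all expected obstetric GAs in Greater London, an allowance that covers both ineligibility and refusal. State the uptake among eligible women that this implies.
2. Apply an eligible share to 3,225 before the 70%, from the network's audit data if available and otherwise as a stated range. Give the resulting sample, and update the expected event counts in section 12.2.2 to match.

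In either case replace 88% with the exact-binomial power for the resulting sample or range, and give the critical number of events and the actual alpha.

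This is a change of text only. It needs no extra enrolment, data or procedures. The cost is a less favourable stated figure: a power of about 79–80% if 2,250 is kept, or an expected sample below 2,250 if the deduction is made.

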The Pan-London Perioperative Audit and Research Network (PLAN): [name], [name], [name], [name], [name], [name], [name], [name], [name], [name], [name], [name], [name], [name], [name], [name], [name], [name], [name], [name], [name], [name], [name], [name], [name].

Web: www.uk-plan.net

Statistician:

[name] and [name]

DREAMY Research Team:

Designated collaborators, Clinical Trials Assistants and/or Research Nurses for the DREAMY study. Led by [name].

3 Protocol synopsis

| | |
|--------------------------------------|--|
| Official title: | Direct reporting of awareness in maternity patients: a prospective evaluation of accidental awareness under general anaesthesia in obstetric surgery patients |
| Brief title /Acronym: | DREAMY |
| Sponsor reference number: | 16.0063 |
| Public database trial ID: | TBC |
| Research Question | What is the incidence of AAGA (accidental awareness under general anaesthesia) using a Brice questionnaire in obstetric anaesthesia in the UK? |
| Study design | Observational non-interventional |
| Eligibility criteria: | Inclusion criteria: 
 1. Female adults (≥ 18 years) of $\geq 24/40$ gestation 2. Receiving general anaesthesia (de novo or regional anaesthesia converted to GA) for surgery with an obstetric indication |
| | Exclusion criteria: 
 1. Patients too unwell or confused to be able to complete the questionnaire 2. Patient refusal 3. General anaesthesia for non-obstetric indication (e.g. colorectal or orthopaedic surgery in a pregnant patient) 4. Surgery ≥ 48 hours post-partum 5. Unable to communicate verbally/in writing in English language |
| Anticipated start date | February 2017 |
| Anticipated end date | February 2019 |
| Target number of participants | 2250 |
| Primary aim | Establish the incidence of AAGA using a Brice questionnaire in obstetric anaesthesia in the UK |

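### The stated 88% power does not belong to the exact binomial test named; at 2,250 participants that test has about 79–80% power

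*Protocol*

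**What the plan says.** Section 12.2.1 builds the expected sample from London births, the proportion having a general anaesthetic, an uplift of 1.12 for procedures other than caesarean section, and 70% recruitment. It calls the result "equivalent to a point estimate of ~2250 included participants over 12 months". The synopsis (section 3) gives 2250 as the target number of participants.

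The section then describes the study's purpose: "This is a descriptive observational study with the intent of capturing data from as many eligible participants over a 12 month study period as possible". One power statement follows. The incidence to be detected is "at least three times the incidence described in the overall surgical patient population", with that population's incidence given as 0.15% or 1:660. The power is reported as "using an exact binomial test and one-sided α of 0.05 is 88" per cent.

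The same section plans an analysis with post hoc power calculations at 12 months. Possible extension of the study depends on the confidence interval width and on whether a significant comparison with earlier incidences can be made.

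**The concern.** The sentence names the test, the significance level, the reference incidence and the multiple to be detected, and the sample size stands just above it. The power can therefore be recomputed without any assumption. Case counts are small: about 3.4 expected under the reference incidence and about 10 under three times that. With so few cases the cut-off moves in whole cases, and one case more or less changes power by 8 to 9 points. A power taken from a normal approximation, or from a cut-off one case too low, can then be well away from that of the exact test.

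This is the protocol's only power statement, and it concerns the primary endpoint. An inflated figure makes the study look more certain to pick up a threefold incidence than it is. It also sets a misleading benchmark for the 12-month decision on extension, because a correct exact calculation made then would seem to fall short for reasons unrelated to the data.

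**Working it through.** **Inputs, all from section 12.2.1**

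- Sample size n = 2,250 (unrounded: 0.70 × 3,225 = 2,257.5).
- Reference incidence p0 = 0.0015, or 1/660 = 0.001515. The protocol gives both, so both are carried through.
- Alternative p1 = 3 × p0 = 0.0045, or 3/660 = 0.004545 (1:220).
- Exact binomial test, one-sided α = 0.05.

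**Expected cases**

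- Reference: 2,250 × 0.0015 = 3.4; 2,250/660 = 3.4.
- Alternative: 2,250 × 0.0045 = 10.1; 2,250 × 3/660 = 10.2.

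**Reproducing 88%**

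The one-sample normal approximation without continuity correction is

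power = Φ{ [ (p1 − p0)√n − 1.645 √(p0(1 − p0)) ] / √(p1(1 − p1)) }.

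- p0 = 0.0015: Φ(1.175) = 88.0%.
- p0 = 1/660: Φ(1.186) = 88.2%.

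So 88% is recovered, but by an approximation and not by the exact test.

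**The exact test**

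Step 1: find the smallest r with P(X ≥ r | n, p0) ≤ 0.05. Step 2: power = P(X ≥ r | n, p1).

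| Reject at | Size, p0 = 0.15% | Power, p1 = 0.45% | Size, p0 = 1/660 | Power, p1 = 3/660 |
|---|---|---|---|---|
| ≥ 6 | 0.1262 | 93.8% | 0.1305 | 94.1% |
| ≥ 7 | 0.0559 | 87.8% | 0.0584 | 88.4% |
| **≥ 8** | **0.0221** | **79.1%** | **0.0233** | **80.0%** |
| ≥ 9 | 0.0079 | 68.2% | 0.0084 | 69.3% |

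Seven cases exceeds 0.05 under either reference, so the cut-off is 8. The shortfall is 88 − 79.1 = 8.9 points or 88 − 80.0 = 8.0 points. The type II error is 20.9% or 20.0%, against 12% implied. The cut-off of 7 also gives about 88%, but it holds 5% only as a mid-p test (mid-p 0.039 to 0.041), which the protocol does not name.

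**Could another reading give 88%?**

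- n = 2,257 or 2,258: 79.4% to 80.3%.
- n = 2,880 (expected deliveries under general anaesthetic): 89.9% to 90.5%. n = 3,225 (all eligible): 91.3% to 91.9%. Neither is the included sample, and neither gives 88%.
- Other methods at n = 2,250: continuity-corrected normal 84.6% to 84.8%; arcsine 85.3% to 85.6%; Poisson 79.1% to 80.0%; Wald 68.5% to 68.9%.
- Exact power is saw-toothed in n. From 1,500 to 2,449 participants it stays below 87%. It first reaches 88% at n = 2,503 (1/660) or n = 2,528 (0.15%), and falls below again when the cut-off moves to 9: 84.9% at n = 2,650 (1/660) and 85.5% at n = 2,700 (0.15%).

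**What 2,250 participants detect with 88% power**

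Solving P(X ≥ 8 | 2,250, p) = 0.88 gives p = 0.00506, about 1:198. That is 3.34 times 1/660, or 3.37 times 0.15%.

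**The case against.** The arithmetic is not in dispute; the argument is about weight. The power figure did not set the sample size. The target comes from birth counts and a 70% recruitment aim, the study calls itself descriptive, and power is reported afterwards. The corrected figure is still about 80%, a conventional level. The primary analysis in section 12.2.2 is a proportion with a binomial confidence interval, set against three hypotheses (1:660, 1:152 and 1:19). The threefold alternative, 1:220, is none of these. With the same cut-off of 8 cases, power is about 98% at 1:152 and essentially 100% at 1:19. The protocol also says the final number may be lower or higher than 2,250, and a sample a little above 2,500 would reach 88%.

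All of this stands as a limit on the consequences. It does not make the sentence right. The protocol attaches 88% to a named exact test at the expected sample size, and that test does not yield it. Variation in recruitment works both ways: at n = 2,200 the exact power is 77% to 78%. The mid-p reading may explain where 88% came from, but the document does not show its origin and mid-p is not what it specifies.

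**Conclusion.** The stated power is wrong for the stated test. With 2,250 participants, one-sided α of 0.05 and a reference of 0.15% or 1:660, the exact binomial test rejects at 8 or more cases, has an actual size of 2.2% to 2.3%, and has 79.1% or 80.0% power for three times the reference. The protocol overstates power by 8 to 9 points. The result uses only the protocol's own inputs and holds for both forms of the reference incidence and for 2,250 to 2,258 participants. It takes 2,250 as the expected sample size because that is the only figure given for included participants. The sentence must be corrected. The recruitment target, the endpoints and the comparison with the 1:152 and 1:19 hypotheses are not put at risk.

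**What to change.** Replace the power sentence in section 12.2.1 with wording such as: *With 2,250 participants, an exact binomial test at one-sided α 0.05 (reject at 8 or more cases; actual size 2.2% to 2.3%) has about 80% power if the incidence is three times the reference of 0.15% (1:660).*

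Two alternatives are acceptable:

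- Keep 88% and restate the detectable incidence as about 1:198 (3.34 times 1/660, or 3.37 times 0.15%).
- Keep 88% for a threefold incidence but name the method that produced it. If that was the cut-off of 7 cases, state its actual size of 5.6% to 5.8%.

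The replacement sentence above is preferable to either alternative because it keeps the exact test, which suits counts this small. Use the same method for the 12-month calculation so that the two figures can be compared. It would also help to add that power at 1:152 is about 98%.

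The cost is one sentence and a less favourable figure. Recruitment, data collection and the planned analysis do not change, and the target in the synopsis stays as it is.

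### Extension after 12 months may depend on whether the comparison with published incidences is significant, with no limits set, so the type I error of that primary comparison is not controlled

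*Protocol*

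**What the plan says.** Section 12.2.1 (estimated sample size) expects "equivalent to a point estimate of ~2250 included participants over 12 months". The power statement refers to an incidence "at least three times the incidence described in the overall surgical patient population", with the reference put at 0.15% or 1:660, and is derived "using an exact binomial test and one-sided α of 0.05 is 88" per cent.

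The same section then states: "Analysis and post hoc power calculations will be taken at the 12 month threshold". The purpose is "potentially extending the study dependent upon the confidence interval width of the identified AAGA proportion and ability to make a statistically significant comparison" with incidences already documented. Two triggers are therefore named: interval width, and whether significance can be shown. No numerical value is attached to either, and no upper limit is placed on the extension.

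In section 12.2.2 (primary endpoint analysis) the AAGA proportion "will be expressed using binomial confidence intervals and compared with established values". Three candidate rates, 1:660, 1:152 and 1:19, are to be compared by Fisher's exact or chi-squared "testing to yield a definitive answer as to which is the most likely hypothesis of the three".

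**The concern.** If recruitment stops when a test is significant and continues when it is not, the test gets a second chance to reject a true null hypothesis. Its overall type I error then exceeds that of a single test at the same final sample size, unless the levels are adjusted. The clause makes the decision to continue depend on the primary result itself and leaves the number of repetitions open.

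The protocol does call the study descriptive. However, it also sets an alpha, claims power, makes significance a criterion for extension and promises a definitive choice among three rates. Error control is thus a standard that it sets for itself. At stake is whether a final statement that the obstetric rate differs from a published one can be read at its stated level, or is open to the charge that recruitment went on until significance appeared.

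Post hoc power is a side issue. Computed at the observed rate it adds nothing to the p-value, so it cannot guide the decision that it is paired with.

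**Working it through.** **Inputs from the protocol.** First-look size n₁ = 2,250; exact binomial test, one-sided 0.05; reference rates p₀ = 1/660, 1/152 and 1/19.

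**Assumptions, because the protocol gives no values.** There is one extension of 25%, 50% or 100% of n₁ (563, 1,125 or 2,250 women). It is triggered whenever the test against the given p₀ is not significant, and the retest uses the same nominal level.

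**The plan's own figure.** At n = 2,250 and p₀ = 1/660 the smallest count with P(X ≥ r) ≤ 0.05 is r = 8, with actual level 0.0233. Power at 3/660 is P(X ≥ 8) = 0.800 (level 0.0221 and power 0.791 with p₀ = 0.0015). The stated 88% is not reproduced by the exact test. It matches a normal approximation (0.880 to 0.882), or r = 7, whose level of 0.056 to 0.058 exceeds 0.05. That is a separate point. What matters here is that the first look against 1:660 spends only 2.3% of the nominal 5%.

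**Formula for one extension.** With critical counts r₁ at n₁ and r₂ at the final N, and X₂ the events among the added women:

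overall error = P(X₁ ≥ r₁) + Σ over x < r₁ of P(X₁ = x) · P(X₂ ≥ r₂ − x).

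For p₀ = 1/660 and a doubling, r₁ = 8 and r₂ = 12, which gives 0.0233 + 0.0326 = 0.0559. A single test at N = 4,500 has error 0.0454, so the extra look adds about 1.05 percentage points.

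| Reference rate | One look at 2,250 | Extended by 25% / 50% / 100% | Single test at the final N |
|---|---|---|---|
| 1:660 | 2.3% | 3.6% / 4.4% / 5.6% | 3.0% / 3.6% / 4.5% |
| 1:152 | 4.7% | 5.8% / 6.7% / 6.9% | 3.7% / 4.4% / 3.9% |
| 1:19 | 4.6% | 6.2% / 7.0% / 7.3% | 4.4% / 4.8% / 4.5% |

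Without discreteness, the normal limit at nominal one-sided 0.05 is 6.9%, 7.4% and 8.0%. A two-sided one-sample chi-squared test with a 50% or 100% extension gives 5.0% or 6.5% (1:660), 7.0% or 7.5% (1:152) and 7.4% or 8.0% (1:19).

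**Repeated extensions.** Against 1:660, with further blocks of 2,250 and the exact test, the error is 5.6% after one extension, 6.8% after two and 8.2% after three.

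**Intervals.** The rule examined is to extend if the lower 95% limit does not exceed 1/660, by 50% or 100%. Clopper-Pearson coverage is 96.4% or 95.4% at a true 1:660, 97.4% or 97.8% at 1:152, and 95.8% for both at 1:19. A Wilson interval at a true 1:660 with a doubling covers 93.6%, against 94.6% at fixed N. Extending on width alone, with assumed targets of 0.004 to 0.007, kept Clopper-Pearson coverage at 95.0% or above.

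**What an adjusted level would do.** For two equal looks the normal limit needs about 0.030 one-sided per look to hold 0.05 overall (0.033 for a 50% extension). With the exact test at 0.03 against 1:660 and a doubling, the thresholds are 8 and 13 events. Overall error is then 3.7% and power at three times the reference is 0.97. With a 50% extension these are 3.0% and 0.92.

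**The case against.** The strongest objection concerns the trigger. The clause can be read as extending only if the study cannot tell the published rates apart, rather than whenever a true rate is not rejected. On that reading an extension would seldom occur. At the expected counts of 4, 15 and 118 events in 2,250, the exact 95% intervals (0.05% to 0.45%, 0.37% to 1.10%, 4.36% to 6.25%) each contain only one of the three rates. At a true 1:152 the test against 1:660 fails only 2.0% of the time. This stands as a limit on the figures, which would overstate the error on that reading. It does not remove the point, because the protocol does not say which reading applies.

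Secondly, retesting at the same level is not written in the protocol, and a separate analysis plan might adjust it. That also stands, and is why the level is listed as an assumption. But the significance trigger itself is fixed in the protocol, and an adjustment is valid only if looks and limits are set in advance.

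Thirdly, against 1:660 the conservatism of the exact test absorbs much of the inflation: extensions of 25% and 50% stay below 5%. That is correct. It does not carry over to 1:152 or 1:19, where every extension size tried exceeds 5%.

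A reader might also infer that every later test and interval is compromised. The documents do not support that. The trigger concerns the AAGA proportion and published incidences, not the PCL-5 comparisons or the factor associations of section 12.2.3. Exact intervals kept their coverage; the protocol says only that intervals are binomial, so the small loss seen with Wilson is a caution, not a finding. Nor does post hoc power inflate error by itself. An argument that the width criterion favours low estimates needs absolute width, which the protocol does not specify. Relative to the estimate the order reverses: the width is about 2.3 times the estimate at 4 events and 0.36 times at 118.

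**Conclusion.** The concern holds for the primary comparison with published incidences. Extension conditional on significance, without a cap, fixed looks or an adjusted level, leaves its type I error uncontrolled. Under the stated assumptions, one extension brings the overall one-sided exact error to between 3.6% and 5.6% against 1:660, and to between 5.8% and 7.3% against the other two rates. In every case this is above the error of a single test at the same final size. It grows with repetition, for which the protocol sets no limit.

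The size is modest and depends on the extension size, the retest level and the reading of the trigger, none of which the protocol fixes. It does not show that 5% is exceeded in every case, that exact intervals fail, or that secondary analyses are affected. The clause should be corrected because it ties continued recruitment to the result and the correction is cheap.

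**What to change.** In section 12.2.1, delete the ability to reach significance, and the post hoc power calculation, from the extension rule. Base any extension on one of two grounds: enrolment below the planned 2,250 at 12 months, or a target confidence interval width stated in advance (absolute or relative) with a maximum sample size. Precision-based extension suits a descriptive study and need not be given up. Naming an exact interval in section 12.2.2 would settle the coverage question.

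If a significance-based extension is to be kept, prespecify the number of looks, the maximum sample size and the adjusted level for each reference rate compared. About 0.03 one-sided per look serves for two equal looks. Thresholds of 8 and 13 events at 2,250 and 4,500 cover 1:660 only, so the other two rates need their own.

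The cost is one paragraph of protocol text. The downside is that the investigators lose the freedom to extend on a borderline result.
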